6.3 Medications Allowed During the Trial

Youth in both conditions may receive medical and/or psychiatric evaluations at any point prior to or during the study. If it is deemed appropriate by medical staff, youth may receive medication for concomitant physical or psychological problems. Youth and family members who are taking medication at baseline will not be excluded from the study. BSFT actively works with families to encourage them to seek medical guidance when it appears to be necessary. Thus, in BSFT, adolescents as well as other family members may receive medications as needed.

7.0 MEASUREMENTS, EVALUATIONS, AND ANALYTICAL METHODS

7.1 Identification and Screening

For parent guardians and adolescents that appear to meet the protocol's inclusion/exclusion criteria, CTP staff members will briefly describe the protocol and ask for permission to make a referral to the research assistant. The research assistant will briefly explain the study to the parent guardian, and ask their permission to ask the screening questions. Parent guardians must also give verbal permission to speak with adolescents, other children under 18, and other family members before any screening of adolescents or informed assent/consent procedures with adolescents or other family members are initiated. Research assistants will query to identify key family members that play an important emotional or instrumental role in the life of the adolescent and family. Eligible participants will be informed about the nature of the study, and will be asked about their level of interest in being part of the protocol.

The research assistant will be trained in relevant aspects of the protocol, including identification of prospective participants and determination of inclusion/exclusion criteria. Ongoing supervision for adherence and retraining if needed of the research assistants on protocol procedures will be conducted by each Node.

7.2 Informed Consent

Informed consent/assent procedures are also described in Section 4.3. After routine screening, the research assistant will explain all aspects of the study to eligible participants, including risks, benefits, randomization, interventions, videotaping sessions, assessments, duration, and reimbursement. Eligible participants will be encouraged to ask questions about any aspect of the study. The research assistant will also ask questions to assess individuals' understanding of the key issues mentioned above. Following clear indications that eligible participants understand the study they will be asked to sign the consent/assent forms.

7.3 Inclusion/Exclusion Criteria Review

Participants will be 480 (or more) adolescents ages 12 to 17 inclusive, who used illicit drugs, other than alcohol or tobacco, in the last month or that is referred from an institution (e.g. detention, residential treatment, court) to the CTP for the treatment of drug use.

Participants' family members will also be included in the study. Recruitment will be focused on including a minimum of 100 female and 200 minority adolescents (100 African American and 100 Hispanic). Participants will be included if they are age 12 to 17 inclusive, and have used any illegal drug in the 30-day period preceding the baseline assessment or if they were referred from an institution (e.g. detention, residential treatment, court) to the CTP for the treatment of drug use. Adolescents must currently live with or be expected to live with formal or informal "family". Adolescents must reside in the same geographical area as the CTP following randomization. Adolescents will be excluded if they are expected to live in a halfway house, institution, independent or assisted living facility, foster care, or in a location outside of the CTP's geographical area.

7.4 Enrollment Procedures

Based on preliminary data from the Adolescent Snapshot Interview, the current flow of cases at interested CTPs indicates that CTPs should have no difficulty meeting the expected number of cases for this study. However, if there are any difficulties recruiting cases, additional advertisements may need to be included. All advertisements will be approved by the appropriate IRBs.

7.5 Prevention of Study Dropouts

As part of their consent/baseline assessment, participants will complete a list of three persons to contact in case the research assistant is unable to find the participants. The participants will be asked for specific consent to contact the individuals on this contact list for tracking purposes only. In the

event that these individuals need to be contacted, research assistants will not reveal any confidential information about the reason for seeking the whereabouts of the participant. The only information research assistants will provide is that the participant listed the individuals name and number in case they were unable to be reached in the future. Moreover, to prevent further attrition from the study, all participants will be reminded of assessments, interviews, and/or appointments by phone the week prior to their scheduled time/day. An SOP with a brief script for research assistants will be developed for these purposes. Also, CTPs are encouraged to send holiday and birthday cards to participants as a way of maintaining participation in both conditions. Finally, the monetary incentives for completing follow-up assessments also serve to increase participation.

7.6 Overview of Assessments

Timing of Assessments

Assessment of primary outcomes will be conducted at baseline (B1) and monthly post-randomization (T1-T12). Secondary outcomes will be conducted at four timepoints: baseline, 4-, 8-, and 12- months following randomization.

- The baseline assessment will be completed within approximately 2 weeks but not more than three weeks from adolescent assent.
- The 4-month assessment will correspond roughly with the end of BSFT, while the 8-month and 12-month assessments will occur at roughly 4-months and 8-months after the completion of BSFT.

Determining Who Participates in the Assessments

Only a biological parent or legal guardian can give consent for participation of the youth in the study. However, other adults may also participate in the study. Research assistants will follow a standard procedure for determining which parent figures (in addition to the target adolescent) to ask to participate in the study. Parent figures may be selected based on one or more of the following criteria. The family member 1) is biologically related to the youth; 2) lives in the same home as the youth; or 3) serves a functional leadership role (i.e., monitoring/supervision, discipline, financial support) with regard to the youth. This selection will be made prior to the informed consent process, so that all potential participants can be included in the informed consent process.

However, it is possible that adolescent participants may experience a change in caregivers during the course of the study (e.g., moves in with grandmother or other parental adult). Consequently, the issue of which family members to include in assessments will be re-evaluated by the research assistant before each follow-up assessment. If there are no changes in caregiving relationships, the same caregiver should complete the follow-up assessments. An SOP will be developed to provide guidance with regard to which family members should be included in each assessment. Parent figures or any family members who are new to the study will be required to provide informed consent before participating in assessment (or treatment). Only the adolescent and her/his primary caregiver will be included in the formal assessments. Therapists in BSFT will consent additional family members that may be included in therapy sessions.

Confidentiality During Assessments

Adolescent and family member reports on assessments will be kept strictly confidential, including confidential from each other. The only exceptions are in cases of imminent danger, including suicidality, homicidality, abuse or neglect. Similarly, self-reports, interviews, and biological data collected from an adolescent as part of the research protocol will not be shared with parents or any outside agency, unless in instances of suicidality, homicidality, abuse or neglect. This requirement applies in particular to protecting the release of research data to outside agencies (such as the juvenile justice system), which is of great importance when working with a “prison” population. The research assistant will remind participants about the confidentiality of reports as well as their limitations. Parent

[name]

guardians will be informed that information conveyed by adolescents during the assessments is strictly confidential, and that they will NOT have access to this information (except in the instances of imminent danger mentioned above). Adolescents will also receive the same assurances of confidentiality. Emphasizing confidentiality is particularly important for ensuring accurate reports of adolescent drug use and other problem behaviors. At each assessment time point (B1-T12), once the administration of the measures is finalized, Research Assistants will present the following statement to the adolescent: “I have faith that the information I have provided will be kept confidential”. Adolescents will rate this statement using a five-point Likert scale as follows: strongly agree, agree, neutral, disagree, and strongly disagree. This will allow proper monitoring for faith in confidentiality. Sometimes, as treatment progresses, faith in confidentiality of information increases, and adolescents report more drug use.

Baseline Assessments

Baseline assessments will be completed to assess functioning and behaviors prior to entering treatment. Table 1 shows the measures that are administered at baseline. Measures are briefly described below.

Post-randomization Assessments

Primary outcome assessments are conducted monthly and at 4-, 8-, and 12-months following randomization. Secondary outcome measures used in the baseline assessment are also administered at 4-, 8-, and 12-months following randomization as indicated in Table 1.

7.7 Assessment Battery

Measures were selected to examine the study’s primary and secondary hypotheses. In addition, measures were selected to provide basic demographic information about family members and the family. Measures are also included to obtain information (e.g., parent drug use) that may be useful in interpreting results. Table 1 summarizes the measures included in this study, providing information about informant, administration time – separately for parent and adolescent, and domain assessed.

As noted in Table 1, some measures were selected from the CTN Common Assessment Battery. The measures are briefly described below. Measures are described within the domain/area that is being assessed. Copies of the actual measures are found in Appendix B.

7.7.1 Demographics

The CAB Demographic measure is used to characterize the participants. In addition, a family demographic form was added to provide information about aspects of the family that is not contained in the CAB and that may be useful in interpreting the results.

- CTN Demographics Form. The CTN Demographics Form (Common Assessment Battery).
- Parent Demographic Form. This 20-item questionnaire identifies who lives in the adolescent’s home, serve in important familial roles as well as identifies family composition/type and family household income.
- Family Demographic Form. This measure is an interview for parents/guardians at B1, T4, T8 and T12. The purpose of this measure is to identify who resides in the home with the adolescent as well as family members or other individuals that have regular contact with the adolescent. This form also tracks changes in family constitution along the study.

TABLE 1. MEASURES

INSTRUMENT	ADMIN MODE	PARENT TIME (MIN)	ADOL. TIME (MIN)		TIMEPOINT	DEMO-GRAPHICS	PSYCH FUNC.	DRUG USE	EXTERNALIZING BEHAVIOR	INTERNALIZING BEHAVIOR	FAMILY	PEER
CTN COMMON ASSESSMENT BATTERY												
CTN Baseline Demographics Form	Interview	--	10'		B1	X						
Urine drug screen	Assay	--	5'		Monthly, B1 - T12,			X				
Risk Behavior Survey	Interview	--	10'		B1, T4, T8 & T12				X			
Addiction Severity Index-Lite- Drug Abuse module only	Interview	10'	--		B1 & T12			X				

TABLE 1. (CONTINUED) MEASURES

INSTRUMENT	ADMIN MODE	PARENT TIME (MIN)	ADOL. TIME (MIN)		TIMEPOINT	DEMO-GRAPHICS	PSYCH FUNC.	DRUG USE	EXTERNALIZING BEHAVIOR	INTERNALIZING BEHAVIOR	FAMILY	PEER
PROTOCOL SPECIFIC ASSESSMENTS												
Parent Demographic Form	Interview	10'	--		B1, T4, T8, T12	X						
Family Demographic Form	Interview	5''			B1, T4, T8, T12	X						
DISC Predictive Scales	Interview	15'	15'		B1 & T12		X		X	X		
DISC SA	Interview	--	30'		B1 & T12							
Timeline Follow Back	Interview	--	30'		Monthly, B1 - T12,			X				
National Youth Survey	Interview	--	10'		B1, T4, T8 & T12				X			
Parenting Practices (Chicago Survey)	Self-report	20'	20'		B1, T4, T8 & T12						X	X
Family Environmental Scale	Self-report	5'	5'		B1, T4, T8 & T12						X	
Conventional Activities of friends (Pittsburgh survey)	Self-report	5'	5'		B1, T4, T8 & T12							X
Peer delinquency Scale	Self-report		5'		B1, T4, T8 & T12							X
Youth Self Report	Self-report	--	20'		B1, T4, T8 & T12				X	X		
Adverse Events+	Interview	5'	5'		B1, T4, T8 & T12							

7.7.2 Drug Use (Hypothesis 1)

Hypothesis 1: BSFT will be significantly more effective than TAU in reducing adolescent drug use defined as the percentage of drug use days in 28-day periods. The Time Line Follow Back is used as the measure of outcome. Biological measures are included to improve the veracity of adolescent self-reports.

- Substance Abuse Assays. *Urine drug screens* will be conducted at all assessment points (administered by research assistant). The urine drug screens will be used at each assessment point to improve the veracity of self-reports. Sensitivity of detection of drugs varies greatly with the dose taken. Sensitivity can be affected by the quantity of fluids a person takes in prior to a urine void, whether the urine void is the first of the day after waking or not, whether the individual is a chronic user, and the individual's natural body metabolism. Urine analysis can detect cocaine and opioid use for 2 to 3 days. Marijuana can be detected for 10 days and even up to 30 days for chronic users. Benzodiazepines can be detected up to 14 days. Barbiturates can only be detected for 3 days but Phenobarbital up to 2 weeks. PCP is detected for 3 to 8 days. LSD is detected in urine up to 2 days. Urine assays will monitor the use of marijuana, opioids, cocaine, amphetamines, methamphetamines, benzodiazepines, PCP, and barbiturates. Assessment staff will be trained in appropriate observational methods. Urine drug screens will be conducted using the, SureStep Drug Screen Card 10A and urine cups which includes temperature controlled monitoring. The urine assay used in this protocol will be the same as those included in the Common Assessment Battery.
- Timeline Follow Back (TLFB). The TLFB will be used to measure adolescent drug use. At baseline, the TLFB will be used to identify drug use in the 30-day period that precedes the baseline assessment. At T1, the TLFB will assess daily use for all days between randomization and the T1 assessment. At T2 and through T12 the TLFB will be used to collect data on daily use from the prior assessment to the current assessment. Thus, the TLFB will be used to collect 365 continuous days of data on daily drug use after randomization.

The TLFB has been adapted for use with adolescents (Bry & Krinsley, 1992; Bry et al., 1986; Liddle et al., 1997). The TLFB method obtains retrospective reports of daily drug use by using a calendar and other memory prompts to stimulate recall. It gathers daily information on specific drugs used and amount of use, (number of drinks, hits, rocks, etc.). The TLFB yields consistently high test-retest correlations over periods of up to 1 year (Carey, 1997; Mason et al., 1994), and has been shown to correlate with other self-reports as well as with collateral reports (Sobell & Sobell, 1992).
- C-Diagnostic Interview Schedule for Children, Substance Abuse /Dependence Module (DISC SA/D). The computerized generic DISC will be used to diagnose substance abuse or dependence. Developed by Shaffer and colleagues (1996), the DISC generic is a highly structured diagnostic interview designed for use by non-clinicians to assess mental health diagnosis. DISC adheres tightly to DSM-IV criteria. A scoring algorithm permits diagnosis to be established based either on symptom criteria alone or symptom criteria and a minimum level of diagnosis-specific impairment. Test-retest reliability and validity of DISC 2.3 have been found moderate to good in multiple samples (Schwab-Stone et al., 1996). The DISC 2.3 has been shown to be in high agreement (ranging from 0.69 to 0.99) with the ICD –10, DSM-III-R, and DSM IV (Hasin et al., 1997).

7.7.3 Engagement in Treatment Sessions (Hypothesis 2a)

Hypothesis 2a: BSFT will be significantly more effective than TAU in engaging adolescents and family members in treatment.

Engagement in treatment will be captured using the service activity logs for clinical services that are completed for sessions in both conditions. Information from agency service activity logs will be captured on the Study Termination CRF.

7.7.4 Adolescent Externalizing Problems (Hypothesis 2b)

Hypothesis 2b: BSFT will be significantly more effective than TAU in decreasing externalizing behavior problems.

- National Youth Survey. The *Self-Report Delinquency Scale* (Elliot et al., 1983) will be used in testing Hypothesis 2b. This Scale consists of 23 items from the National Youth Survey (Huizinga & Elliot, 1983). Items assess adolescent criminal behavior on five subscales: 1) *Total Delinquency*, 2) *General Theft*, 3) *Crimes Against Persons*, 4) *Index Offenses*, and 5) *Drug Scales*. The instrument is well validated and has been used extensively in prior research. The *Total Delinquency* scale will be used as an indicator of externalizing in Hypothesis 2b.
- Youth Self Report. The YSR is a self-report instrument (Achenbach & Rescorla, 2001) administered to children ages 11 – 18 to describe their own functioning. This instrument is designed to assess the severity of 105 problem behaviors along two scales of social competence: 1) *Activities Scale*: Includes scores for the number of sports, recreational activities, jobs and chores, plus ratings on the amount and quality of participation in the child's various activities; 2) *Social Scale*: Includes scores for participation in organizations, number of close friends, number of weekly contacts with friends, how well the child gets along with others, and how well the child plays and works alone. The YSR is designed to provide standardized descriptions of the child's functioning (Achenbach & Rescorla, 2001). Problem behaviors can be scored along the dimensions of the super-ordinate domains of "internalizing" and "externalizing" behaviors, or along smaller syndromes of behavior problems (e.g., delinquent, aggressive anxious/depressed). The "externalizing" domain will be used as an indicator of externalizing behaviors in Hypothesis 2b.
- Diagnostic Interview Schedule for Children-Predictive Scales. *Externalizing disorders (Oppositional Defiant Disorder and Conduct Disorder)* will be identified using both parent and adolescent report, and will be used as indicators in testing Hypothesis 2b (measure described in 7.7.8).

7.7.5 HIV/Sex Risk Behaviors (Hypothesis 2c)

Hypothesis 2c: BSFT will be significantly more effective than TAU in decreasing adolescent sexually risky behaviors.

- Risk Behavior Survey. *HIV risk* will be assessed using this 9-item questionnaire (CTN Common Assessment Battery; NIDA, 1991). The Risk Behavior Survey (RBS), an abbreviated version of the Risk Behavior Assessment (RBA) developed for a NIDA Cooperative Agreement (NIDA, 1991), will be used to measure HIV and HCV risk behaviors. HIV risk behaviors in the areas of drug use and sex in the previous 30 days are measured. Reliability and validity assessments of the RBS support its adequacy as a research tool for populations of drug users (Needle et al., 1995; Weatherby et al., 1994).

Most CTPs that have expressed interest in our protocol have a standardized procedure for screening HIV risky behaviors at intake. In case Risk is determined (i.e., non barrier use) patients will be counseled to seek HIV testing.

7.7.6 Prosocial Activities (Hypothesis 2d)

Hypothesis 2d: BSFT will be more effective than TAU in increasing prosocial behaviors.

- Pittsburgh Youth Survey. (Loeber et al., 1998). The *Conventional Activities of Friends Scale* will be used to measure prosocial activities of friends. This scale includes 8 questions concerning the number of friends that engaged in prosocial activities. These behaviors range from obeying school rules to participating in religious activities. High scores indicate that most friends engage in these conventional behaviors, and the lowest scores reflect the complete absence of any friends involved in these prosocial and traditional activities. Scale scores are summed for each subject, thereby reflecting the overall degree of exposure to peers engaged in these conventional behaviors. This scale will be used as an indicator of prosocial activities in testing Hypothesis 2d.
- Pittsburgh Youth Survey. (Loeber, 1989). The *Peer Delinquency Scale* will be used to measure affiliation with deviant and delinquent peers. This scale consists of 15 questions that the adolescent rates on a 5-point scale based on the number of friends that have engaged in a variety of antisocial and delinquent behaviors. Behaviors rated range in severity from minor infractions to serious and violent crimes against others. This scale will be used as a negative indicator of prosocial activities in testing Hypothesis 2d.

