2.2 Secondary Hypotheses

Secondary hypotheses examine the relative effectiveness of BSFT over TAU in:

Hypothesis 2a: Engaging adolescents and family members in treatment

Hypothesis 2b: Decreasing adolescent externalizing problem behaviors

Hypothesis 2c: Decreasing adolescent sexually risky behaviors

Hypothesis 2d: Increasing adolescent prosocial activities (e.g., school, work)

Hypothesis 2e: Improving family functioning (e.g., parenting, parent-adolescent relations).

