7.7.7 Family Functioning (Hypothesis 2e)

Hypothesis 2e: BSFT will be significantly more effective than TAU in improving family functioning.

- Parenting Practices Questionnaire of The Chicago Youth Development Study. *Parenting practices* will be measured through 47 questions on parent and adolescent reports (Gorman-Smith, Tolan, Zelli, & Huesmann, 1996). The Parenting Practices Measure, was derived from the parental supervision and discipline interview used in the Oregon Youth Study and Pittsburg Youth Study (Thornberry, Huizinga, & Loeber, 1995). Factor analyses have identified four factors 1) Positive Parenting, 2) Discipline Effectiveness, 3) Avoidance of Discipline, and 4) Monitoring. Positive parenting refers to the use of positive rewards and encouragement of appropriate behavior. Discipline effectiveness is a measure of how effective parental discipline is in controlling the youth's behavior. Avoidance of discipline refers to the parent's avoidance of providing consequences or disciplining for fear of the youth's behavior escalating. Monitoring is a measure of monitoring and involvement in daily activity and routines and knowledge of youth's whereabouts throughout the day. Reports of discipline effectiveness and avoidance of discipline are gathered from parents only. Estimates of positive parenting and extent of monitoring are gathered from both parent and child. Internal consistency reliabilities of each of the subscales ranged from .68 to .81. Confirmatory factor analyses have consistently identified two latent constructs of Discipline and Monitoring which will be the two indicators of parenting used in the family functioning composite (Gorman-Smith et al., 1996). All four factors in this inventory will be used as indicators of parenting practices.
- Family Environmental Scale. The Family Environmental Scale (FES; Moos & Moos, 1986) is a widely used measure that was developed to measure social and

environmental characteristics of families. This measure has been used in thousands of studies to capture critical aspects of family functioning. In this study, we will be using the cohesion and conflict subscales of the FES, administered to both parents and adolescents. Internal consistency reliability estimates for the subscales range from 0.61 to 0.78. Conflict and cohesiveness subscales will be administered to measure family functioning.

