Analysis. The analyses for Hypothesis 2b is identical to the hierarchical linear models (HLM) (Bryk & Raudenbush, 1992) used to test Hypothesis 1. It is anticipated that no link function will be necessary.

Hypothesis 2c: BSFT will be significantly more effective than TAU in decreasing sexually risky behaviors

Outcome variable. For Hypothesis 2c, the total score of the ‘HIV/Sex Risk Behaviors’ measure will be used as the outcome.

Analysis. The analyses for Hypothesis 2c is identical to the hierarchical linear models (HLM) (Bryk & Raudenbush, 1992) used to test Hypothesis 1. It is anticipated that no link function will be necessary. The composite measure will be constructed using the methodology described in hypothesis 2b applied to the items of the Risk Behavior Survey from the Common Assessments Battery.

Hypothesis 2d. BSFT will be significantly more effective than TAU in increasing prosocial activities.

Outcome Variable. A composite measure will be verified using confirmatory factor analysis. Scales to be included in the composite and confirmatory analysis are the ‘Conventional Activities of Friends’ scale of the Pittsburgh Youth Survey, and the (negatively weighted) ‘Peer Delinquency’ scale from the Pittsburgh Youth Survey.

Analysis. Hypothesis 2d will be analyzed as in Primary Hypothesis 1 using hierarchical linear models (HLM) (Bryk & Raudenbush, 1992). Again, the composite measure will be constructed using the methodology described in 2b.

Planned Post-hoc Analyses. Planned post-hoc analyses for the secondary hypotheses are identical to those explained above under the primary hypotheses. These analyses will attempt to explain the variability in the treatment effect.

Hypothesis 2e. BSFT will be significantly more effective than TAU in improving family functioning.

Outcome Variable. The four components of the ‘Parenting Practices Inventory’ will be used to create a composite for use in this analysis. The four component scales from the Parenting Practices Inventory are ‘Positive Parenting’, ‘Discipline Effectiveness,’ ‘Avoidance of Discipline’ and ‘Monitoring’ scales from the Pittsburgh Youth Survey (see Gorman-Smith et al., 1996).

Analysis. Hypothesis 4 will be analyzed as in Hypothesis 1 using hierarchical linear models (HLM) (Bryk & Raudenbush, 1992). Again, the composite measure will be constructed using the methods described in 2b, above.

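### Hypothesis 2d is about the adolescent's own prosocial activities but is scored only on friends' behaviour, and Sections 7.7.7 and 10.3 disagree on the Hypothesis 2e composite

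*Protocol*

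**What the plan says.** **Hypothesis 2d.** Section 2.2 gives "Hypothesis 2d: Increasing adolescent prosocial activities (e.g., school, work"; Sections 10.1 and 10.3 repeat it with employment in place of work. Section 7.7.6 assigns two scales from the Pittsburgh Youth Survey. Conventional Activities of Friends "will be used to measure prosocial activities of friends. This scale includes 8 questions concerning the number of friends that engaged in prosocial activities". The Peer Delinquency Scale has 15 questions on friends' antisocial acts and serves as a negative indicator. Section 10.3 builds the composite from these two scales and no others, and adds: "A composite measure will be verified using confirmatory factor analysis".

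**Hypothesis 2e.** Section 2.2 gives "Hypothesis 2e: Improving family functioning (e.g., parenting, parent-adolescent relations". In Section 7.7.7 one sentence speaks of "two latent constructs of Discipline and Monitoring which will be the two indicators of parenting used in the family functioning composite", and the next says that all four Parenting Practices factors serve as indicators. The same section adds, for the FES: "Conflict and cohesiveness subscales will be administered to measure family functioning". In Section 10.3 the four Parenting Practices components "will be used to create a composite for use in this analysis", and the FES is not mentioned.

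**Other scales collected.** Section 7.7.4 describes a Youth Self Report (YSR) Activities Scale: "Includes scores for the number of sports, recreational activities, jobs and chores", with ratings of how much and how well the child takes part. Table 1 schedules the YSR and the FES at B1, T4, T8 and T12, which are all the secondary-outcome assessments.

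**The concern.** A secondary hypothesis is only as good as the variable that carries it. For 2d, an adolescent who goes back to school or takes a job but keeps the same friends would score no change. One who changes friends and does nothing else would score as improved. A significant result would then be reported as support for a hypothesis that was not tested.

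For 2e, an analyst who follows Section 7.7.7 and one who follows Section 10.3 could build different composites. That choice should not remain open once data by condition exist. The omitted part also matters to this trial: Section 1.3.4 treats family interaction as the main target of the therapy, and Section 5.2.1 counts reduced parent-adolescent conflict among its aims.

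**Working it through.** The plan gives no figure to reproduce here. The check sets each hypothesis beside its indicators, then counts parameters for the factor model.

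**1. Hypothesis against outcome**

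| | Stated construct (2.2) | Measures section (7.7.6, 7.7.7) | Analysis section (10.3) |
|---|---|---|---|
| 2d | Adolescent's own activities | Two friends scales | The same two friends scales |
| 2e | Parenting and parent-adolescent relations, as examples | Two parenting constructs, then four factors; FES cohesion and conflict also listed | Four parenting scales only |

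- 2d: 2 of 2 indicators concern friends and 0 concern the adolescent's own activity. Section 7.7.6 itself interprets the first score as exposure to conventional peers and the second as affiliation with delinquent ones. Table 1 files both under the peer domain.
- 2e: 4 of 4 indicators in Section 10.3 are parenting practices; 0 of the 2 FES subscales enter. The phrase in Section 7.7.7 about the indicators of parenting within the family functioning composite suggests that the composite was meant to hold something besides parenting.

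**2. What is already collected.** The YSR and FES are scheduled at 4 of 4 secondary assessments, the FES for both parent and adolescent. The YSR Activities Scale, as described, covers jobs, chores, sports and recreation but has no school item. The YSR Social Scale covers participation in organizations, but also credits the number of close friends and contacts with them. That is not clearly prosocial when Section 7.7.6 counts delinquent peers against the adolescent.

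**3. The factor-analytic check on the 2d composite.** Section 10.3 applies the 2b method: reliability with loadings fixed at 1 and, if that is insufficient, factor scores from estimated loadings. For two scales fitted alone:

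- Observed moments: 2 variances + 1 covariance = 3.
- Free loadings, factor variance fixed: 2 loadings + 2 residual variances = 4 parameters. 4 > 3, so the model is not identified.
- Loadings fixed at 1: 1 factor variance + 2 residual variances = 3 parameters. Degrees of freedom = 3 − 3 = 0.

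With 0 degrees of freedom the fit rules in Section 10.1.1 (Comparative Fit Index below .95, or standardized root mean squared residual above .06) have no misfit to detect. Fitted alone, the model cannot verify the composite, and the factor-score fallback is unavailable.

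**The case against.** Several stronger readings are tempting, and the protocol does not support them.

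- *The 2e outcome does not measure its hypothesis.* Parenting is the first example that 2e names, and four parenting scales measure it. The outcome is narrower than the hypothesis, not off it.
- *The FES data go unused.* Sections 10.1.1 and 10.2.6 use baseline family and peer functioning as covariates and effect modifiers, and the FES could supply them. What is missing is a stated place for it in the 2e outcome.
- *Avoidance of Discipline will cancel real improvement.* Section 7.7.7 describes an adverse construct, and Section 10.3 gives it no sign, although it signs Peer Delinquency. But the scoring direction is not given in the text at hand. A reversed scale would also lower the reliability that must be sufficient before equal weights are used, and the fallback would then estimate its loading. The sign should be stated; harm is not shown.
- *The 2d factor analysis can never fail.* That holds only if the composite is fitted alone. Section 10.1.1 plans a factor analysis of all constructs. If this means a joint model, a two-indicator factor correlated with others is identified. The reliability check can fail in either case.
- *The earlier trial's cohesion result sizes the loss.* F(1, 72) = 6.66 gives 2·√(6.66/72) = .61 SD with equal arms. With 50 and 24, as t(49) and 74 − 50 imply, it gives √(6.66 × (1/50 + 1/24)) = .64. Neither measures any harm from the 2e definition, and the protocol does not say that the FES was the instrument.

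These points limit the 2e and factor-model criticism. None answers the main one: both 2d indicators are about friends.

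**Conclusion.** The point holds for 2d without qualification: 0 of 2 indicators measure the stated construct, in the measures section and the analysis section alike. It holds for 2e as an inconsistency and a partial gap: Sections 7.7.7 and 10.3 define different content, and the outcome omits parent-adolescent relations. The factor-model objection is conditional on a stand-alone fit.

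The protocol defines both outcomes, so this is not detail properly deferred to an analysis plan. The consequence is confined to what may be concluded from two secondary hypotheses. No effect on power or type I error is claimed, and Hypothesis 1 is untouched. The conclusion assumes that the scales contain what Sections 7.7.4, 7.7.6 and 7.7.7 say they contain.

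**What to change.** Make these changes before any outcome is examined by condition.

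1. **2d, choose one.** (a) Score it on the YSR Activities Scale, say that the school example remains unmeasured, and report the two friends scales as a separate peer-affiliation outcome. (b) Keep the friends scales, restate 2d as a peer-affiliation hypothesis, and limit its conclusion to that.
2. **2e.** Write one composite, identically, in Sections 7.7.7 and 10.3. Either include FES cohesion and conflict, or restate 2e as parenting practices and give the FES its own stated role. State the sign of each adverse scale (conflict, Avoidance of Discipline).
3. **Composite check.** If the friends composite is kept, do not rely on a stand-alone two-indicator factor model to verify it. Keep the reliability check.

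No new instrument or visit is needed. Option (a) adds one secondary outcome and requires confirming that the Activities Scale will be scored, since the protocol names only the YSR externalizing and internalizing domains for use. Option (b) costs a narrower hypothesis.
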